## 21 APPENDIX D: INSTRUCTIONS FOR RETINAL AMYLOID IMAGING

NeuroVision Imaging, LLC is providing the equipment and software analysis for retinal amyloid imaging.

### 21.1 Pupil dilation will be conducted prior to imaging.

Administer:

1. Proparacaine 0.5% - numbing – 1 drop OU -wait 2 minutes
2. Tropicamide 0.5% (Mydracil) –1 drop OU– wait 3 minutes
3. Phenylephrine HCl 2.5% - 1 drop OU – wait until dilated >3.5 mm

### 21.2 Imaging Procedure

The imaging shall use the Retia device with software version 1.4.5 or later.

For each study scan, capture autofluorescence images of the Superior field in 3 focal plans, up to 6 images each

#### a. Image set 1 of 3

- i. First image – Full automatic IR and AFL of superior field.
- ii. Images 2 to up to 6

1. Review the fully automatic IR image and read/record the machine diopter set point (to the tenths digit, e.g. 2.4)

2. Start a new exam, select Superior, and then go to Manual Alignment and Focus mode

a. Use the slider and joystick buttons to enter the previously recorded autofocus value to the nearest tenth of an MD.

b. Use the on-screen buttons and take one IR and then the sequence of 5 AFL images (one every 5 -10 seconds, the LED cycle time).

#### b. Image set 2 of 3

i. Without exiting the exam,

ii. Move the focus point -2 MD using the slider and/or the joystick buttons (e.g. if the initial focus point was 2.4, then move the focus point to 0.4).

iii. Use the on-screen buttons to take one IR and then the sequence of up to 6 AFL images, one every 5 or so seconds.

#### c. Image set 3 of 3

i. Without exiting the exam,

ii. Move the focus point +4 MD (+2 MD from the original recorded focus point, 4.4 in our example here) using the slider and/or the joystick buttons.

iii. Use the on-screen buttons to take one IR and then the sequence of up to 6 AFL images.

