### 3.2 Primary Endpoints

Change in standard uptake values (SURV) as measured by Florbetapir PET at baseline and 3 months and Retinal Amyloid Index (RAI) as measured by amyloid levels in the retina.

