## 4 STUDY PLAN

### 4.1 Study design

This is a single center, open label, proof of concept, out-patient study. Subjects will undergo Florbetapir PET and have retinal amyloid levels measured, receive an infusion of IVIG at 0.4 g/kg every 14 days for a total of five infusions, and repeat PET and retinal amyloid measures three months after the first infusion.

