## **14 STATISTICAL ANALYSIS**

### **14.1 Primary endpoint**

Graphs of individual changes in standard uptake ratio values (SURV) of Florbetapir PET will be compared between baseline and 3 months. Graphs of individual changes in RAI values will be compared between baseline and 3 months.

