## **15 SAMPLE SIZE**

Five subjects will be included. If it appears that IVIG shows changes in these two markers, a large trial will be considered.

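### Individual RAI changes are to be read from graphs with no measurement-error yardstick, although Appendix D already takes repeat images that could supply a minimum noise band

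*Combined protocol and SAP*

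**What the plan says.** The primary endpoints in Section 3.2 include the "Retinal Amyloid Index (RAI) as measured by amyloid levels in the retina". No formula, unit, eye or rule for combining images is given. The whole RAI analysis in Section 14.1 is one sentence: "Graphs of individual changes in RAI values will be compared between baseline and 3 months".

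Section 15 sets the size and the next step: "Five subjects will be included", and "If it appears that IVIG shows changes in these two markers, a large trial will be considered". No threshold defines a change. Section 4.1 describes the design: "This is a single center, open label, proof of concept, out-patient study". Every subject receives IVIG. Appendix C mentions placebo, but Section 4.1 has no such arm.

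Section 21.2 (Appendix D) asks for repeat images of one retinal field in each session: "capture autofluorescence images of the Superior field in 3 focal plans, up to 6 images each". In the first set, after one fully automatic image, the operator is to "take one IR and then the sequence of 5 AFL images", 5 to 10 seconds apart at the recorded focus. For the second set the instruction is "Move the focus point -2 MD using the slider and/or the joystick buttons", and the third set is taken at +2 MD from the recorded focus.

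No repeatability figure, smallest detectable change, second baseline scan or noise threshold for RAI appears in the document.

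**The concern.** In a controlled trial the comparison arm shows how far a marker moves without treatment. Here there is none, the Background calls the retinal scanner novel, and a reader of the graphs is not told what size of change repeat measurement alone would produce. An ordinary fluctuation could therefore be read as an effect of IVIG.

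Two conclusions rest on that reading: whether a larger trial is considered (Section 15), and whether amyloid reduction explains the apparent effect on brain atrophy (Section 16). The repeat images in Section 21.2 could inform the reading, but Section 14.1 makes no use of their spread.

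**Working it through.** **Inputs.** There are 5 subjects (Section 15) and two retinal sessions each, at screening and month 3 (Section 1), so 10 sessions. Images per session are as in Section 21.2. Section 15 gives no calculation to reproduce. The document gives no RAI standard deviation, so a limit in RAI units cannot be computed, and sizes below are multiples of an error SD.

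**1. Direction of change with no effect.** Assume each RAI value is equally likely to rise or fall, independently across subjects. The number falling is Binomial(5, 0.5).
- All 5 fall: 1/32 = 3.1%.
- At least 4 fall: (5 + 1)/32 = 18.75%.
- At least 3 fall: 16/32 = 50%.

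These describe RAI alone. If the two markers are independent, at least 4 of 5 fall on both with probability 0.1875² = 3.5%, and on at least one with probability 1 − 0.8125² = 34.0%.

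**2. Size of change with no effect.** Let SEM be the SD of a session's RAI on repeat measurement, with normal errors. A difference of two sessions has SD √2 × SEM, so P(|change| > c × SEM) = 2[1 − Φ(c/√2)] = p, and the chance for at least one of five is 1 − (1 − p)⁵.

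| c | One subject | At least one of five |
|---|---|---|
| 1 | 48% | 96% |
| 1.5 | 29% | 82% |
| 2 | 16% | 57.5% |

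The usual 5% limit is 1.96 × √2 = 2.77 SEM. Even with a correct SEM, at least one of five crosses it with probability 1 − 0.95⁵ = 22.6%, and at least two with probability 2.3%.

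**3. What a band from within-session images can support.** Images seconds apart miss the error added between visits by new dilation, alignment and focusing, and possibly by a different software version, since Section 21.2 fixes only a minimum version. Let the between-session SD be r times the single-image SD, and suppose RAI were the mean of m images. A within-session band is then falsely crossed by one subject with probability 2[1 − Φ(1.96/√(1 + m r²))]. Both r and the averaging rule are assumptions.

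| RAI formed from | r = 0 | r = 0.5 | r = 1 | r = 2 |
|---|---|---|---|---|
| 1 image | 5% | 8% | 17% | 38% |
| mean of 6 | 5% | 21.5% | 46% | 70% |
| mean of 18 | 5% | 40% | 65% | 82% |

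The more images are averaged, the narrower the band becomes relative to the true error. A change inside it is small even against the smallest plausible error. A change outside it proves nothing by itself.

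**4. Which images are replicates.** Set 1 mixes one automatic image with five manual ones, so it has five like-for-like images. Sets 2 and 3 have up to six each, at other focus settings. Per eye and session that is at most 4 + 5 + 5 = 14 degrees of freedom, or 140 over 10 sessions if all three settings enter RAI. Set 1 alone gives at most 4 × 10 = 40. No minimum number of images is set: with two per plane the total is 3 × 1 × 10 = 30.

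**The case against.** The strongest reply is that this is a five-subject descriptive proof of concept, that a large trial would only be considered, and that a limit built from images taken seconds apart may mislead more than none. Much of this stands. No formal test or sample-size calculation is needed, and step 3 shows that the band could pass noise as change if crossing it were treated as a finding. That restricts how the band may be used. It does not supply the missing yardstick.

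Other limits also stand. The document does not say that the software can score single images, or how images become one RAI value. Dividing an image SD by the square root of the number of images is right only if RAI is their mean.

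Several stronger readings are tempting and not supported:
- *Any non-zero RAI change triggers a larger trial.* Section 15 refers to changes in two markers and says only that a trial would be considered. The 19% is not the probability of a wrong decision.
- *A change beyond the band is a real RAI change.* The band omits visit-to-visit error, and there is no control group.
- *Many pooled replicates make a better yardstick than the spread of the five changes.* These are different quantities. The spread of the changes includes visit-to-visit error and real subject differences, and for a mean change that is the relevant variance. It fails only as an individual limit.
- *The imaging procedure is at fault.* The acquisition in Section 21.2 is not defective. The gap is in Sections 14.1 and 15.

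**Conclusion.** The concern holds in a limited form. Sections 14.1 and 15 read individual RAI changes, in five uncontrolled subjects, with nothing to show what measurement error alone would produce. With no IVIG effect, at least 4 of 5 RAI values fall with probability 19%, taking RAI alone and assuming rises and falls equally likely and independent. A change above 1 SEM occurs by noise in 48% of subjects, assuming normal errors.

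The repeat images already taken can support a lower bound on the noise, provided single images can be scored and the route from images to RAI is known. They cannot establish that a change beyond that bound is real. The size of the band in RAI units is unknown from the document. The change should be made because it adds a reference line to graphs already planned and needs no extra imaging.

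**What to change.** Amend Section 14.1 as follows, if the vendor software can score single images:
- Estimate the within-session SD from the Appendix D repeat images, using only images taken at the same focus and in the same mode, and only the focus settings that enter RAI.
- Convert it to a session-level error in the way RAI is actually formed from the images, and state that rule.
- Draw ±1.96 × √2 × that error on each subject's RAI graph, labelled as a minimum noise band that omits visit-to-visit error.
- Use it in one direction. A change inside the band is reported as not distinguishable from measurement error and is not counted in Section 15 as evidence of an RAI change. A change outside it is not by itself evidence of an IVIG effect.

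If single images cannot be scored, use a between-session repeatability figure from the vendor. Failing that, state that RAI noise is unknown and that individual changes will not be read as a treatment effect.

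The cost is a per-image export from the vendor and one calculation. The downside is that some apparent changes will be reported as within noise.

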## **22 Amendment 1**

- NewGam 10% changed to Octagam 10%
